NCT04088097

Cognitive Behavioral Therapy for Adolescent Binge Eating and Loss of Control Eating

Document date: 3/13/2024

HRP-503B – BIOMEDICAL RESEARCH PROTOCOL
(2017-1)

Protocol Title: Development and Initial Efficacy Testing of a Cognitive-Behavioral Intervention to Treat Adolescent Binge Eating

Principal Investigator: [name]., Assistant Professor in Psychiatry

Version Date: Version 9 (2/28/2024)

(If applicable) Clinicaltrials.gov Registration #: NCT04088097

SECTION I: RESEARCH PLAN

1. **Statement of Purpose:** State the scientific aim(s) of the study, or the hypotheses to be tested.

The overall aim of the study is:

1. To develop a cognitive-behavioral therapy (CBT) that treats adolescent binge/loss-of-control (LOC) eating and test whether this new CBT for adolescent binge/LOC eating is superior to an active control group.

Hypothesis 1: Adolescents randomized to CBT will have a greater reduction in binge/LOC eating (episode frequency) than adolescents in the active control group.

Hypothesis 2: Adolescents randomized to CBT will have a greater reduction in weight (BMI z-score using measured height and weight) than adolescents in the active control group.

2. **Probable Duration of Project:** State the expected duration of the project, including all follow-up and data analysis activities.

Development and evaluation of the treatment is expected to occur over 6 years (including follow-up and data analysis).

3. **Background:** Describe the background information that led to the plan for this project. Provide references to support the expectation of obtaining useful scientific data.

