Retention, attrition and completion rates will be carefully tracked and reviewed. This will be done quarterly to highlight any possible concerns and will be reviewed formally with the PI and Safety Monitor annually. Differential dropout across treatments and/or higher than expected dropout will be reviewed to determine whether any problems are present and what, if any, corrective action needs to be taken. "Trigger points" for corrective action, as described below, include: 35% ("low alert"), 40% ("mid alert"), 45% ("high alert"), and 50% ("extreme alert"). With early alerts to problems, action

would be taken to avoid higher level alerts; if a higher-level alert should arise, more drastic actions would be taken.

It is possible that baseline differences between the treatment conditions, excessive attrition, and/or missing data will limit the value of the data analysis, and hence knowledge to be gained from this study. For these reasons, interim analyses will be conducted twice yearly. Baseline differences, if present, will be considered in relation to potential effects on the power to detect differences in the primary outcomes. If these effects were to develop and be sizeable, alterations to the randomization schedule would be considered. Such effects would be evaluated and discussed by the PI and mentors, and plans would be communicated to the NIH and Yale IRB. To address excessive attrition and missing data, the following actions would be taken at the “trigger point” for each level of alert:

- 1) Low-level alert (35%): Review of potential problems by PI and review of procedures for supervision of study clinicians.
- 2) Mid-level alert (40%): Meeting between PI and senior study team members to discuss approaches to minimize further dropouts.
- 3) High-level alert (45%): Meeting between PI and senior study team members to determine further alterations to study protocol to complete the study with no further losses.
- 4) Extreme-level alert (50%): In the unlikely event that a 50% dropout rate occurs prior to the mid-study time point, the PI and senior study team members would convene to discuss the usefulness of continuing the study.

It is possible that other situations could occur that might warrant stopping the trial. Any concerns would be discussed with appropriate parties (PI, Mentors, Safety Monitor, NIH, Yale IRB).

Measurement and Reporting of Adverse Events

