Study participant safety will be monitored by the study team and reported to the PI at all visits and referrals will be provided if warranted and/or requested. If a study participant experiences any psychiatric symptoms or distress (e.g., depressive symptoms or suicidality) at any stage of study participation they will receive short-term treatment and support from the study treatment team (which includes psychologists) and will be connected to a local emergency department and their physician or therapist for ongoing care.

Other Potential Issues Relating to Stopping Rules for the Pilot RCT Include:

- 1) **New Information:** It is unlikely that any new information would become available during this trial that would necessitate stopping the trial. If new data become available, these will be evaluated.
- 2) **Limits of Assumptions:** It is possible that baseline differences between the treatment conditions, excessive attrition, and/or missing data could limit the value of data analysis. Baseline differences across treatment groups, if present, will be evaluated twice yearly and considered in relation to potential effects on the power to detect differences in the primary outcomes. If these effects were to develop and be sizeable, alterations to the randomization schedule would be considered. Any plans to alter the randomization scheme would be communicated to the NIH.
- 3) **Limits of Rules:** There are other situations that could occur that might warrant stopping the trial and/or including a section on the safety report entitled “Other situations that have occurred since the last safety report that warrant discussion” to allow for communication of concerns.

13. **Statistical Considerations:** Describe the statistical analyses that support the study design.

DATA ANALYSIS AND AIMS

Baseline demographic and clinical characteristics will be compared between treatment and control groups using chi-square tests for categorical variables (e.g., sex) and ANOVAs or Kruskal-Wallis tests for continuous variables (e.g., BMI z-score). Continuous variables will be examined for adherence to normality using probability plots and Kolmogorov-Smirnov tests. If normality is not satisfied and transformations do not achieve acceptable normality, alternative strategies (e.g., nonparametric) will be considered. Dropouts and completers will also be compared. Analyses will be intent-to-treat. Outcomes will be tested at the $\alpha=0.05$ threshold.

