Overall analysis strategy. Descriptive statistics will quantify change and mixed-effects models (106, 107) will compare treatments through post; 3-month follow-up will be exploratory. These models allow for different numbers of observations per participant, use all available data on each participant, account for clustered data observations, and are unaffected by data missing at random. A further advantage is the capacity to test and account for individual-difference contributions to treatment outcomes (108). This strategy provides flexibility in modeling the correlation structure of the data. In models for each outcome, we will include fixed effects of time and treatment and their interaction, and random subject-level effects. Because we cannot *a priori* predict the shape of the response over time, we will first treat time as categorical and then test for polynomial trends. We will consider different error structures (e.g., compound symmetry, autoregressive) and select the best-fitting structure based on information criteria. Data on all participants enrolled in the study will be used in mixed models. We will compare dropout patterns and if there are concerns of informative dropout and/or informative intermittent missing data, we will use pattern mixture models to perform sensitivity analyses to main analyses.

Primary Aims.

Primary Aim 1 is to **test** the efficacy of adolescent CBT relative to the active control condition at post-treatment on clinical outcomes, including: (a) reduction in binge/LOC eating frequency (evaluated by the QEWP), and (b) reduction in weight (evaluated by BMI z-score). Significant time-by-treatment effects with significantly less adolescent binge/LOC eating and significantly reduced weight in adolescent CBT relative to the control condition will be considered supportive of these aims. Parallel analyses will also assess binge/LOC frequency reduction using the EDE; because this interview is only administered at baseline and post, this analysis will, by definition, occur among completers. Adolescent CBT is hypothesized to yield reduced binge/LOC eating frequency and weight reduction (i.e., weight loss or less excess weight gain) compared to the control group.

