Primary Aim 2 is to **test** the acceptability and establish the feasibility of adolescent CBT. Descriptive statistics will quantify clinician/patient treatment ratings, sessions attended, and retention, and clinician adherence/competence through ratings of recorded sessions.

Secondary Aims.

Secondary Aim 1 is to **explore** the efficacy of adolescent CBT relative to active control: (a) reduction in disordered eating thoughts and behaviors (EDE-Q), (b) improvements in executive function (S-Upps, Kirby), (c) improvement in psychosocial functioning (reduced depression, PHQ; improved self-esteem, RSES).

Secondary Aim 2 is to **explore** the durability and maintenance of treatment effects during short-term follow-up.

Secondary Aim 3 is to **explore** potential predictors of primary outcomes. Following Kraemer's (109) conceptual/statistical model for predictors, we will explore whether baseline characteristics predict treatment effects by testing for main effects and interactions in models for primary outcomes (specified above), including (a) adolescent executive function (S-Upps, Kirby), (b) self-weighing (EARLY), (c) parent BMI and disordered eating behaviors (EDE-Q/QEWP), and (d) parent feeding practices and attitudes (CFQ). [name] et al (25) used this analytic strategy in earlier work.

Power Analysis and Justification of Sample Size. Results are anticipated to yield significant impact by providing effect sizes for grant applications to perform definitive studies comparing the new adolescent CBT treatment with existing interpersonal therapy for youth LOC. Power estimates for the pilot RCT were based on the comparison of CBT (n=25) and control conditions (n=25). Assuming a two-sided test at $\alpha=0.05$ threshold, we have 80% power to detect clinically meaningful between-subjects ($d=0.8$) and within-subject effects within each group ($d'=0.58$). Even assuming 20% dropout, we still have 80% power to detect clinically meaningful effects ($d=0.9$ between-subjects and $d'=0.66$ within-subject). While power is limited given the pilot nature of the study, such effects are similar to effects observed in a prior study (31) that compared LOC eating between youth who received either interpersonal therapy or were in a control group. Thus, we have a reasonable chance of finding statistically significant differences between CBT and control, even in this pilot study.

SECTION II: RESEARCH INVOLVING DRUGS, BIOLOGICS, RADIOTRACERS, PLACEBOS AND DEVICES
--

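### Does Primary Aim 1 need a stated rule for the case where only one of its two outcomes is significant?

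*Combined protocol and SAP*

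**What the plan says.** The Statement of Purpose (Section I, item 1) opens with one overall aim, to develop the therapy and "test whether this new CBT for adolescent binge/LOC eating is superior to an active control group". Two numbered hypotheses sit under it. Hypothesis 1 concerns binge/LOC episode frequency. Weight has its own: "Hypothesis 2: Adolescents randomized to CBT will have a greater reduction in weight (BMI z-score using measured height and weight").

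Section I, item 13 (Statistical Considerations) sets the threshold: "Outcomes will be tested at the $\alpha=0.05$ threshold". The overall analysis strategy then works outcome by outcome: "In models for each outcome, we will include fixed effects of time and treatment and their interaction". Primary Aim 1 lists (a) binge/LOC frequency on the QEWP and (b) BMI z-score. Its one sentence on interpretation, which rests on the time-by-treatment interaction, reads in part: "significantly less adolescent binge/LOC eating and significantly reduced weight in adolescent CBT relative to the control condition will be considered supportive of these aims".

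The power paragraph says of the 25 versus 25 comparison that "we have 80% power to detect clinically meaningful between-subjects" effects of d = 0.8, or d = 0.9 after 20% dropout. It names no outcome. Its only precedent concerns eating: "such effects are similar to effects observed in a prior study (31) that compared LOC eating". The Data and Safety Monitoring Plan (item 12) says that baseline differences between arms will be "considered in relation to potential effects on the power to detect differences in the primary outcomes".

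**The concern.** The interpretive sentence joins the two outcomes with a conjunction and stops there. Read strictly, it makes both results necessary. Read with the separate hypotheses, it lets each stand alone. Neither reading is spelled out for a trial in which CBT beats control on binge eating but not on weight, or the reverse. The opening aim asks a single question about superiority, so the same split data could be described as superior or as not superior, with the choice made after the results are known.

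The power paragraph adds to the doubt. A reader could take 80% as the chance of success on the whole aim, when it covers one comparison. The supporting precedent is for LOC eating, so nothing shows that d = 0.8 is plausible for BMI z-score. The monitoring plan nevertheless refers to power for the primary outcomes in the plural when it discusses possible changes to the randomization schedule.

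**Working it through.** **Inputs from the protocol (item 13):** 25 per arm; two-sided alpha 0.05; d = 0.8 between groups; 20% dropout, leaving 25 × 0.8 = 20 per arm, with d = 0.9; within-group d' = 0.58 and 0.66.

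**Inputs assumed, because the documents do not give them:** the true effect on each outcome, and the correlation ρ between the two outcomes, taken as 0 to 0.8. Two-sample t-tests stand in for the planned mixed models, whose power inputs are not stated.

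**Step 1: the plan's own figure.** The noncentrality is d × √(n/2).

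- 25 per arm, d = 0.8: 0.8 × √12.5 = 2.83. Power is 80.7% by the normal approximation and 79.1% by the noncentral t.
- 20 per arm, d = 0.9: 0.9 × √10 = 2.85. Power is 81.2% and 79.2%.
- Paired t within group: 79.5% (n = 25, d' = 0.58) and 79.9% (n = 20, d' = 0.66).

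The stated 80% reproduces, as the power of one comparison.

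**Step 2: two outcomes.** With single-outcome powers p1 and p2,

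P(exactly one) = p1 + p2 − 2 × P(both).

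At ρ = 0 with p1 = p2 = 0.7915, P(both) = 0.7915² = 0.626 and P(exactly one) = 1.583 − 1.253 = 0.330. For other ρ, P(both) comes from a bivariate normal with its margins set to the t-test power.

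| Scenario (binge d / weight d) | Power, each outcome | Exactly one, ρ = 0 / 0.3 / 0.5 / 0.8 | Both, same ρ |
|---|---|---|---|
| 25 per arm, 0.8 / 0.8 | 79%, 79% | 33.0 / 27.6 / 23.2 / 14.6% | 62.6 / 65.4 / 67.5 / 71.9% |
| 20 per arm, 0.9 / 0.9 | 79%, 79% | 32.9 / 27.5 / 23.2 / 14.5% | 62.7 / 65.5 / 67.6 / 71.9% |
| 20 per arm, 0.8 / 0.8 | 69%, 69% | 42.5 / 34.8 / 29.0 / 17.9% | 48.1 / 52.0 / 54.9 / 60.4% |
| 25 per arm, 0.8 / 0.5 | 79%, 41% | 55.2 / 48.7 / 44.5 / 39.2% | 32.5 / 35.7 / 37.8 / 40.5% |
| 25 per arm, 0.8 / 0.3 | 79%, 18% | 68.7 / 64.7 / 62.7 / 61.2% | 14.2 / 16.2 / 17.2 / 18.0% |

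A simulation of 60,000 trials with pairs of correlated t-tests gave 33.1 / 27.6 / 23.6 / 14.9% for the first row. Outside the chosen range of ρ, the first-row chance of exactly one is about 37% at −0.3 and about 10% at 0.9. The last two rows use weight effects chosen for illustration; neither is in the protocol.

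**Step 3: does any reading require a different analysis?**

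- *Each hypothesis judged alone.* Each test has its own 0.05 and its own 80%. A split result is read off directly, and nothing needs recalculating.
- *Both required for one overall claim.* Requiring both needs no alpha adjustment. The relevant power is the last column, 63% to 72% in the first row.
- *Either sufficient for one overall claim.* Familywise error would be up to 1 − 0.95² = 9.75% if the outcomes were independent.

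Only the second and third readings change a number, and both presuppose one overall verdict. Item 13 plans no such test. It has separate hypotheses behind it, a model for each outcome, and an interpretive sentence that speaks of effects and aims in the plural. The first reading is the one the text supports.

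**The case for a change.** The best case for a change is that Aim 1 is set to test efficacy while the secondary aims only explore, that the protocol claims a reasonable chance of significant findings, and that the opening aim poses one superiority question. Separate testing does not say how that question is answered when the hypotheses disagree. A split is not remote: 15% to 33% in the most favourable scenario, and more if the weight effect is smaller. One added sentence would cost nothing.

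Part of this stands. No sentence covers the split result, and no effect or precedent specific to weight is given.

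The rest is weaker. In the scenario built on the protocol's own d, the usual result is both outcomes significant; a split becomes the more likely result only under smaller effects or a smaller sample than that scenario uses. The power statement is in standardized units and tied to no outcome, so its detectable effects apply to BMI z-score as much as to binge eating. What is missing is evidence that such a weight effect is plausible. The monitoring plan asks for a judgement about baseline imbalance, for which the detectable d of 0.8 or 0.9 can serve either outcome. A sentence barring any overall superiority claim from one significant outcome would also do more than record the separate reading. For that claim it is a both-required rule, with joint power of 63% to 72% under the stated assumptions. Finally, the protocol itself says that power is limited in a pilot and that the results are to supply effect sizes for definitive studies, so a formal win rule matters less here.

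**Conclusion.** No change follows. The omission is real, but the plan's structure fills it: a split result supports one numbered hypothesis and not the other, and a competent analyst would report it that way. The stated 80% is correct for a single comparison (79% by the noncentral t). Writing the separate reading down would alter no test, alpha level, test order or sample size.

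The split-result figure of about 33% to 15%, with joint significance in about 63% to 72%, rests on d = 0.8 on both outcomes, 25 per arm with no dropout, a correlation of 0 to 0.8, and t-tests in place of the mixed models. The documents state neither a common true effect nor a correlation, so the range illustrates the issue and is not a forecast. The lack of a precedent for weight is a limit on how far the power statement reassures about Hypothesis 2. It is not an error in the statement.

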Focus groups will be audio recorded and transcribed. If participants decline permission for recording, they can participate in general activities and can provide written responses to the focus group questions that will be shared anonymously with the group, but cannot be present at the focus group.

Assessments. Parents and adolescents will be assessed. At the beginning of treatment, adolescents will undergo a clinical assessment to confirm eligibility and to inform the course of treatment. Assessment batteries are guided by recommendations of *NIH ADOPT* workgroup on core measures (e.g., QEWP, EARLY, BRIEF, Kirby, PSS) (62-66). As well as established measures, acceptability (sessions attended; retention; patient/ clinician ratings of content), and adherence (e.g., homework completion), will be assessed. We will also gather clinical data on the patient's medical history prior to the study, which we will update as indicated in Table 2. Assessments will be the same for the open-series of patients during the treatment development phase as well as during the RCT phase, except that there will be no follow-up to the open-series of patients.

Assessment Training: Independent outcomes assessors will receive training in diagnostic interviews from investigators following well-established protocols used in previous projects. Once interviewers are certified in the measures (MINI and EDE), they will receive ongoing supervision to ensure consistent use and prevent drift.

TABLE 2: Assessment Batteries

	Baseline	Month 1	Month 2	Month 3	Post	Follow-Up (3 mo)
Adolescent assessment battery						
Established interviews:						
Eating Disorder Examination interview	*				*	
MINI Psychiatric Interview (MINI)	*					
Medical history	*					
Established survey measures:						
• Short UPPS (S-UPPS)	*				*	
• Amsterdam Executive Function Inventory (AEFI)	*				*	
• Kirby Delay Discounting	*				*	
• Sensitivity to Reward/Punishment (SRSPQ)	*				*	
• Questionnaire for Eating and Weight Patterns (QEWP-5)	*	*	*	*	*	*
• Eating Disorder Examination—Questionnaire (EDE-Q)	*	*	*	*	*	*
• Patient Health Questionnaire-9 (PHQ-9)	*	*	*	*	*	*
• Rosenberg Self-Esteem Scale (RSES)	*	*	*	*	*	*
• EARLY	*	*	*	*	*	*
• Pubertal Development Scale	*				*	*
• Perceptions of Teasing Scale (POTS)	*	*			*	*
• Weight-related Victimization	*				*	*
• Weight Bias Internalization Scale (WBIS-M)	*				*	*
• Brief Resilience Scale (BRS)	*	*	*	*	*	*
• Self-compassion Scale (SCS)	*	*			*	*

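### The EDE analysis is confined to completers on the ground that two assessment times force it; they do not

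*Combined protocol and SAP*

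**What the plan says.** Section I, item 13 (Statistical Considerations) states a general principle: "Analyses will be intent-to-treat". Under the overall analysis strategy it specifies one model form: "In models for each outcome, we will include fixed effects of time and treatment and their interaction, and random subject-level effects". It says of these models: "These models allow for different numbers of observations per participant, use all available data on each participant". It adds: "Data on all participants enrolled in the study will be used in mixed models".

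Primary Aim 1 names the QEWP for binge/LOC frequency and BMI z-score for weight. A parallel analysis of binge/LOC frequency then uses the EDE, with this limit: "because this interview is only administered at baseline and post, this analysis will, by definition, occur among completers".

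Table 2 confirms that the EDE is given at baseline and post only. The S-UPPS and Kirby measures have the same two marks. Both are efficacy outcomes in Secondary Aim 1, and no completer limit is stated for them. The plan does not define a completer.

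**The concern.** The limit is presented as a consequence of the schedule. If it is not one, participants are left out of the EDE analysis for no valid reason, and a change contrast in those who remain can be biased when loss is related to severity.

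The EDE matters beyond its supporting rank. After baseline it is the only interview measure of binge/LOC frequency in Table 2, and item 4 says: "Independent outcomes assessors will receive training in diagnostic interviews from investigators". The power section says the pilot is to supply effect sizes for later definitive studies, so a biased EDE effect could be carried forward. Item 10 (Risks) also describes one route to outcome-related loss, namely withdrawal from the study after significant deterioration. The documents give no rate for it and do not say whether a post EDE is still sought.

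**Working it through.** **1. The plan's own figures.** Inputs from the power section: 25 per arm, two-sided alpha 0.05, 80% power, 20% dropout. After dropout, 25 x 0.8 = 20 per arm. Solving the two-sample t-test gives detectable d = 0.809 (25 per arm) and 0.909 (20 per arm), which agrees with the stated 0.8 and 0.9. No figure is given for the EDE analysis. At 20% loss it would use about 40 of 50 adolescents.

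**2. Do two times force a completer analysis?** When everyone has both values, the time-by-treatment term is the difference in mean change. With baseline-only records kept, the likelihood estimate of an arm's post mean is

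observed post mean + b x (baseline mean of all - baseline mean of those observed at post),

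where b is the slope of post on baseline. Baseline-only records therefore enter the estimate. As a check, a random-intercept model was fitted to one simulated trial with five lost per arm. It converged on 50 participants and 90 records, against 40 and 80 for completers, and the estimates differed (-1.11 and -0.78). One data set shows only that the records are used, not which estimate is nearer the truth. Item 9 uses the EDE at intake to settle eligibility, so every randomised adolescent should have a baseline value.

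**3. Loss that depends on baseline in one arm, random in the other.** The documents give neither a loss pattern nor correlations. Assumed: roughly normal scale; baseline-post correlation r = 0.4 to 0.7; loss of 20% (power section) or 35%, the first attrition trigger in item 12: "Low-level alert (35%): Review of potential problems by PI and review of procedures for supervision of study clinicians". Losing the most severe share p lowers the baseline mean of those remaining by k = phi(z)/(1 - p), with z the upper-p normal quantile.

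- k = 0.280/0.80 = 0.350 at 20%, and 0.370/0.65 = 0.570 at 35%.
- Completer change bias = k(1 - r). At 20%: 0.350 x 0.6 = 0.210 and 0.350 x 0.3 = 0.105. At 35%: 0.570 x 0.6 = 0.342 and 0.570 x 0.3 = 0.171.
- All-randomised model: the post mean falls by kr and the correction adds back b x k with b = r, so the bias is 0.00. Large simulations agree.

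The bias runs against the arm that loses its most severe participants, and reverses if it loses its least severe. If the odds of loss only double per baseline SD in that arm, it shrinks to 0.08-0.04 (20%) and 0.13-0.07 (35%).

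**4. Loss that depends on later scores.** Assumed: baseline correlates 0.4 with Month 3 and with post; Month 3 correlates rho = 0.4 or 0.7 with post. First, one arm loses its worst Month 3 scores and the other loses at random.

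- Completer change bias = k(rho - 0.4). At 20%: 0.00 and 0.350 x 0.3 = 0.105. At 35%: 0.00 and 0.570 x 0.3 = 0.171.
- All-randomised bias = k(rho - 0.4b). With b = 0.4 at 20%: 0.350 x 0.24 = 0.084 and 0.350 x 0.54 = 0.189. Selection lowers b a little, and simulation gives about 0.08 and 0.20 (35%: 0.14 and 0.32).
- If the unobserved post score itself drives 20% loss in one arm, with r = 0.4 and 0.7, completers are off by 0.21 and 0.105, the all-randomised model by about 0.30 and 0.20.

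In these cases the bias flatters the arm that loses its worst participants, and the all-randomised model is the more biased. The ranking is not fixed, however. If both arms lose those who worsened most from baseline to Month 3, by the same cut-off, neither analysis is biased when there is no true effect. With a true d of 0.8 and 20% lost overall (29.7% of control, 10.3% of CBT), completers show 0.64-0.56 and the all-randomised model 0.72-0.62.

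**5. Precision.** With loss unrelated to baseline, both estimates average about the true value, and the all-randomised standard error is only 1% to 6% smaller. With loss that depends on baseline it can be slightly larger (0.287 against 0.276 at r = 0.7 and 35%, a ratio of 1.04).

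**The case against.** The plan discloses the limit, so one may read it as a specific exception that overrides the general rules. That stands: the fault is a wrong reason for a declared choice, not two rules in unresolved conflict.

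The stakes are also modest. The stated reason suggests that a completer is someone with a post EDE. On that reading no post interview is discarded, only unpaired baselines, and these add almost no precision. Section VI pays for the post assessment and states no condition of treatment completion, which favours retention. A baseline-adjusted analysis of those with a post EDE would also be valid if loss depends only on baseline and arm, although the plan does not specify one.

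The strongest objection is step 4: under some kinds of loss the replacement is worse. That stands too, and is why both results should be shown. The plan's other protection is conditional on concern about informative missingness and refers to the main analyses: "we will use pattern mixture models to perform sensitivity analyses to main analyses". The comparison of dropouts with completers and the attrition alerts describe or monitor loss; they do not bring anyone back into the EDE analysis.

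**Conclusion.** The point holds as an unsound justification in a supporting analysis. Two assessment times do not confine the EDE analysis to completers. The plan's model, and its treatment of S-UPPS and Kirby, show as much.

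The gain is conditional. It is 0.21-0.10 SD at 20% loss and 0.34-0.17 SD at 35% if one arm's loss follows baseline severity under the assumptions of step 3, and less under milder selection. It can be negative if one arm's loss follows interim or post scores. Which applies is unknown.

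A reader might infer three stronger things that the documents do not support:

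- That Primary Aim 1 rests on completers. It is decided on the QEWP and BMI z-score, to which the limit does not apply.
- That the all-randomised model removes dropout bias. Step 4 shows that it may not.
- That withdrawals for deterioration must distort the result. No rate is given, and the protocol rates the risk as minimal.

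**What to change.** In Primary Aim 1, replace the completer clause with: *EDE binge/LOC frequency is analysed in all randomised participants with the same time-by-treatment mixed model (baseline and post), including every post EDE obtained regardless of treatment completion.*

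Keep the analysis of participants with a post EDE as a labelled sensitivity analysis, which also settles what completer means here, and show both results. Report missing post EDEs by arm.

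The change uses the plan's own model and data already scheduled, and makes little difference to precision either way. Its price is the one in step 4, so the plan should say that the two-occasion model does not correct loss driven by interim or post scores. Imputation from the monthly self-reports, or extending the pattern-mixture analysis to the EDE, is optional. No rule on withdrawal or clinical management is proposed.
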